This proposal involves two studies of evidence-based suicide prevention practices triggered by CareSource justice notifications, in a 2x2 factorial design. The **first study** will randomize CareSource's ~43,000 Ohio subscribers who pass through jails over 12 months to receive monthly Caring Contact letters sent by CareSource over a 6-month period or to Care as Usual. The **second study** (running simultaneously) will involve a subset of ~6,000 of the 43,000 subscribers passing through jail who were seen in one of 12 large BH agencies in the 6 months prior to jail detention. Using a stepped wedge design, the 12 agencies will be brought online over time, receiving (a) notifications of jail detentions/releases with instructions for re-engaging clients in services; and (b) training in the Safety Planning Intervention plus notification to use it when a subscriber with past *medically treated* suicide attempts (identified by CareSource through claims data) is released from jail.

Specifically, we plan to examine the following:

Aim 1: Evaluate the effectiveness of the implemented study interventions.

Hypothesis 1a: CareSource subscribers who receive CC letters during the 6-month period will have fewer claims related to suicide attempts than subscribers who did not receive CC letters.

Hypothesis 1b: Provider involvement in the reports, re-engagement, and training (RRT) intervention will be associated with a reduction in subscriber claims related to suicide attempts. Further, the addition of flags and recommendations to provide SPI for individuals with past 12 months claims data identified suicide attempts will further reduce suicide attempts.

Aim 2. Examine the number of outpatient behavioral health claims in the 6 months following the index jail release and number of calls to CMS line as mediators of the intervention/s effects on suicide attempts. Mediation will be revealed by the extent to which the intervention effect parameter estimates change with the addition of the putative mediator. We will use bootstrap methods to estimate 95% uncertainty intervals around the mediated effect.

Aim 3. Examine intervention cost-effectiveness and return on investment. We will examine costs (and savings) in future years for both the Caring Contacts and Reports, Re-engagement, and Training (RRT) components of the proposed study.

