Provider meetings: BH providers who are participating in the RRT Intervention (N=120) will be asked to participate in monthly meetings with the Study PIs and CareSource to talk about their experiences, offer feedback, and help problem-solve challenges. These meetings will be held virtually. Additional personnel, including clinical directors, business managers, and other relevant staff may attend these meetings. These meetings are intended to provide an opportunity for the site to ask us questions, address concerns, work through challenges, etc. Because part of this study is focused on implementation, we will need to have formal review and ratings of the information provided in the meetings. CareSource will record the meetings and provide transcripts of the discussions for analysis. Due to the variation in staff attending the steering team meetings, verbal consent will be obtained prior to the start of each of these meetings. If verbal consent is not received, the meeting will not be recorded/transcribed.

Study Outcomes: All study outcomes will be tracked through the use of claims data. These data include diagnosis, treatment, and billed and paid amounts. Data will be extracted using previously established algorithms for suicide and self-injury research developed by the Mental Health Research Network. This is not medical record data. We will not have access to the patient's health record. CareSource will extract data from their Jail-Medicaid database to examine billing and insurance claims submitted for visits associated with our study suicide-outcomes of interest (suicide attempts, all cause injury and poisoning, outpatient BH visits, calls to CMS line, suicide-related ED visits/hospitalizations, and returns to jail detention).

Training behavioral health providers: The 12 BH agencies who see the largest number of justice-involved CareSource subscribers (approx. 6,000 total annually) will be randomly assigned to four cohorts. All four cohorts will follow the same intervention protocols, but they will begin at Months 4, 6, 8, and 10 of the CC intervention, respectively. As BH agencies are assigned to the RRT condition, they will receive training in reaching out to and re-engaging clients who pass through the justice system, and training in suicide risk assessment (C-SSRS²⁸) and response (SPI²⁹).

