For Aim 1, we will assess total number of subsequent attempts using the already-developed Mental Health Research Network (MHRN) algorithm for extracting MT suicide attempt information from claims data.^{10-12,48-58} The main effectiveness analysis is planned as a comprehensive model (i.e., including all 43,000 subscribers) evaluating Study 1 and Study 2 intervention effects, which provides optimal power and the ability to test interactive effects of interventions. All analyses will covary baseline (i.e., past year) values of dependent variables, and will use days incarcerated in the 6 months after the index jail release as an offset. **MT suicide attempts.** The main analysis framework will be logistic regression with the cumulative risk of a claims-data-identified suicide attempts requiring medical treatment over six months post-release as the outcome. We will secondarily use a negative binomial model and a count outcome for the number of MT suicide attempts. Our models will include robust standard errors due to clustering at the agency level. We will adjust for study month, and include indicator variables reflecting: (1) Study 1 intervention condition (i.e., CC or CAU); (2) inclusion in Study 2; (3) Study 2 intervention condition (i.e., RRT or Control). The ***hypothesis that the Study 1 intervention (CC) reduces suicide attempts*** is evaluated with magnitude and significance of parameter estimate associated with random assignment to the Study 1 intervention. The ***hypothesis that the Study 2 intervention (RRT) reduces suicide attempts*** is tested with the parameter estimate associated with exposure to the level 2 intervention. ***The hypothesis that the addition of flags and recommendations to provide SPI*** for individuals with past 12 months claims data identified suicide attempts (one component of the Study 2 intervention) ***will further reduce suicide attempts*** will be tested through the interaction between past history of suicide attempt and being in the Study 2 intervention condition. Identical analyses will be conducted for the other outcomes (all count outcomes): all cause injury and poisoning, outpatient BH visits, calls to CMS line, suicide-related ED visits/hospitalizations, and returns to jail detention. ***Exploratory.*** We will evaluate the interaction of Study 1 and Study 2 interventions by including an interaction term of the two indicators. ***Moderators.*** We will test sex, race/ethnicity, past suicide attempt (y/n), past 6-month BH visit (y/n), past 12-month arrest (y/n), area Deprivation Index,⁵⁹⁻⁶⁰ Mental Health Professional Shortage Area (HPSA)

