Using the IHI Framework for Going to Full Scale,⁶⁶⁻⁶⁷ this project will focus on sustainability and scalability. We will assess, maximize, and optimize intervention: (1) scalability (per the Intervention Scalability Assessment Tool⁶⁸); (2) sustainability (per the Program Sustainability Assessment Tool⁶⁹⁻⁷⁰) (3) feasibility, acceptability, and appropriateness to providers and systems (per the Acceptability of Intervention Measure,⁷¹ Intervention Appropriateness Measure,⁷¹ and Feasibility of Intervention Measure⁷¹); and (4) actual and recommended implementation strategies (via process mapping and implementation process/case notes).

Statistical power. Assumptions. We conducted a simulation study, allowing for variability in release dates, numbers eligible, and introducing a small intra-cluster correlation (ICC = .01). We assumed 43,000 eligible subscribers for Study 1, with 50% randomly assigned to CC. Based on last year's data, we assumed 6,000 eligible subscribers for Study 2. We expect that ~10% of the 6,000 ($n \sim 600$) will have past suicide attempt identifiable through CareSource claims data. We assumed a six-month risk of suicide attempt 0.05, but past 12-month claims data-identified suicide attempt increases this risk (i.e., .034 in absence of past-year suicide attempt, 0.204 with a past-year suicide attempt, odd ratio (OR) = 5), similar to SPIRIT. **Results.** We ran the simulation model 2001 times. Significance was assessed using a two-tailed type-I error level of 5%. Caring Contacts. We will have 85.6% power to detect an effect equivalent to an OR of 0.89. CC has been found to have much stronger effects than this in previous studies²² suggesting that we are adequately powered for CC. RRT. If we assume an intervention effect for Study 2 of 0.87 OR, we will have 88.3% power to detect this effect. For subscribers with a past year suicide attempt within Study 2 (who will be flagged to receive SPI), we will have 96.4% power to detect an OR of 0.63 (the OR detected for SPI in our previous trial, SPIRIT).⁴⁶ Having superadequate power for this test offsets concerns about providers potentially not providing SPI as instructed in this large, real-world study.

D. Material Inducements

Study 1

Provider focus groups: No material inducements will be provided for BH providers who engage in the focus groups. Providers will complete study-related procedures during work time and are typically not able to accept material inducements.

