 - b. CareSource estimates that about half of their claims are submitted within 30 days of the service date. Adding time to clean and de-identify the data, run the MHRN algorithm on the data, and prepare the DSMB report, we estimate that about half of claims data will be available for safety review within 60 days of the service date. Therefore, at Month 6, the DSMB will have all the cases from Months 1-3, and half of the cases from Month 4 for review. At Month 9, the DSMB will have all the cases from Months 1-6 and half of the cases from Month 7 for review. At Month 12, the DSMB will have all the cases from Months 1-9, and half the cases from Month 10 for review. Then, the DSMB will have a closeout meeting when all study data are available.

Analyzed participant data will be stripped of personal information by CareSource, and will be identified in the project only by numerical codes. Links between these codes and personal identifiable information (e.g. names) will only exist in the CareSource database (which will not be accessible by research staff). The collected data will be stored on secure servers at Butler and MSU, which are consistently used for data hosting needs. The outcomes of interest will include suicide attempts, engagement with outpatient mental health and substance use services, and returns to jail detention. We will report pre-post intervention changes in the outcomes, both unadjusted, and adjusted for participant characteristics

Most data collected during the study timeframe will be entered into an online data management system (REDCap). Data will be stored on backed up, password protected servers. Within each computer system, only those users authorized to access the data for a given study are able to do so.

Data from focus groups and provider meetings will also be shared with the DSMB. Since no adverse effects are anticipated from these participant groups, any significant negative feedback from these participants will be shared with the DSMB.

Data and Safety Monitoring Board (DSMB)

This project will utilize the central Center DSMB. Our analysis plan will be reviewed and approved formally by the DSMB prior to the start of the study.

E. Potential Benefits

There are no direct benefits from participation in this study, but there are potential benefits.

Participating providers will have the opportunity to be trained in how to address suicide risk assessment

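### RRT is randomised across only 12 agencies with no small-sample method named; an uncorrected robust SE tested against 1.96 gives about 8-13% false positives, not 5%

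*Combined protocol and SAP*

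**What the plan says.** Specific Aims (2.A) describes Study 2 this way: "Using a stepped wedge design, the 12 agencies will be brought online over time". Under the heading on training behavioral health providers (2.C2), the agencies "will be randomly assigned to four cohorts", and "they will begin at Months 4, 6, 8, and 10 of the CC intervention, respectively".

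The Data Analysis section (2.C4) plans one "comprehensive model (i.e., including all 43,000 subscribers) evaluating Study 1 and Study 2 intervention effects". For the main outcome, "The main analysis framework will be logistic regression with the cumulative risk of a claims-data-identified suicide attempts requiring medical treatment". The covariates are study month, CC assignment, Study 2 inclusion, RRT condition and the baseline value of the outcome. RRT is tested by its own coefficient, and the added effect of the SPI flags by the interaction of RRT with past attempt. On clustering the section says only: "Our models will include robust standard errors due to clustering at the agency level".

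The Statistical power paragraph of 2.C4 sets the level: "Significance was assessed using a two-tailed type-I error level of 5" per cent. It reports simulated power but no simulated type I error. No section gives the type of sandwich estimator, its degrees of freedom, or how subscribers outside the 12 agencies are to be clustered.

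**The concern.** For RRT the independent units are the 12 agencies, not the 6,000 subscribers. The usual sandwich variance estimates the between-cluster spread from 12 residual sums. It is biased downward because those residuals come from a fitted model, and it is itself variable. Comparing the resulting statistic with 1.96 ignores both problems. The cause is the small number of clusters, so a small ICC does not remove it. Because cohorts are randomised, between-agency differences add variance to the RRT estimate but do not bias it.

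RRT and the added effect of SPI flags together make up Hypothesis 1b. If the level is about twice the stated 5%, p-values and confidence intervals for both are too optimistic, and an ineffective programme could be scaled up on a chance result. The same model is to be used for five further outcomes and for the mediation analysis.

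**Working it through.** **Inputs from the documents.** 43,000 subscribers, 6,000 of them in Study 2 (so 37,000 outsiders); 12 agencies in four cohorts; starts at Months 4, 6, 8 and 10; six-month risk 0.034 without and 0.204 with a past-year attempt; about 10% of Study 2 with a past attempt; CC 1:1; ICC 0.01; two-sided 5%.

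**Assumptions not in the documents.** Three agencies per cohort; the scale of the ICC; agency-size spread (CV 0.58 when unequal); 10% past attempt among outsiders; no agency-by-time variation; no offset in the main runs. ICC 0.01 was read in two ways:
- Latent scale: agency SD = √[(0.01/0.99) × π²/3] = 0.182 on the logit.
- Proportion scale: √(0.01 × 0.05 × 0.95) / (0.05 × 0.95) = 0.459 on the logit.

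**The plan's own figure.** The plan gives no type I error to reproduce. Its nearest figure is 88.3% power for RRT at OR 0.87. An individually randomised comparison of 3,000 v 3,000 at risks 0.05 and 0.0438 gives z = 0.00622/0.00546 = 1.14 and power Φ(1.14 − 1.96) = 20.6%. The 88.3% therefore does not reproduce. That is a separate matter, and the type I error results below do not depend on it.

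**Analytic check.** P(|t| > 1.96) is 7.8% on 10 df and 7.6% on 11 df. If the SE is also too small by √(10/12), these become 10.4% and 10.1%.

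**Null simulation.** Logistic model with month, CC, past attempt, Study 2 and RRT. 5,000 runs per row (4,000 in the last), Monte Carlo error about ±0.8 points. Entries are rejection rates in %. Outsiders are singletons except in the column marked otherwise. KC is Kauermann-Carroll, MD is Mancl-DeRouen.

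| ICC, agency sizes | RRT, uncorrected, 1.96 | Same, outsiders as one cluster | RRT × past attempt, uncorrected | RRT, 12/11 factor + t10 | RRT, KC + t10 | RRT, MD + t10 | RRT, permutation |
|---|---|---|---|---|---|---|---|
| 0, equal | 8.0 | 9.8 | 9.1 | 4.0 | 3.9 | 3.2 | 4.8 |
| Latent, equal | 9.0 | 10.8 | 9.0 | 5.5 | 5.4 | 4.3 | 5.2 |
| Latent, unequal | 9.5 | 11.4 | 10.1 | 5.4 | 4.8 | 3.8 | 5.0 |
| Proportion, equal | 9.2 | 10.4 | 9.4 | 5.3 | 4.8 | 3.7 | 4.9 |
| Proportion, unequal | 11.4 | 12.3 | 10.9 | 6.8 | 6.0 | 4.6 | 5.0 |

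For the interaction, MD with t10 gave 3.9-5.1%.

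**Offset.** Runs with a log(time at liberty) offset (unequal sizes, 1,700 runs each, ±1.5 points) gave, for latent and proportion ICC:
- RRT uncorrected: 9.6% and 11.2%, and up to 12.8% with outsiders as one cluster.
- Interaction uncorrected: 11.1% and 9.6%.
- RRT corrected: permutation 5.2% and 5.3%; KC 4.8% and 6.1%; MD 3.4% and 4.4%.

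**Separately programmed repeats** (2,000 to 2,500 runs per scenario, no offset in the two whose set-up is recorded). The uncorrected RRT rate was 7.5-10.1%, 8.6-10.9% and 8.7-11.5%. With outsiders as one cluster it was 11.9% and 10.2-12.6%. At ICC 0 one repeat gave 9.6% (equal sizes) and 10.6% (unequal).

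**Agency effects are not a substitute.** With agency fixed effects, an uncorrected sandwich and 1.96, the RRT rate was still 7.6-9.4%.

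**The case against.** The strongest reply is that the plan does not commit to an uncorrected estimator or to 1.96. A common version, the G/(G−1) factor with G = 12 and a t reference, roughly holds the level: 4.0-6.8% in the main runs, and up to 7.3% in the repeats. On that view the fault is under-specification, not a wrong test. This stands as far as it goes, and the inflation is conditional.

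It does not make the plan safe. The model includes 37,000 people outside the 12 agencies. If each is entered as its own cluster, G is 37,012, the factor is 37,012/37,011 (about 1.00003) and the t reference is effectively normal. The automatic correction then disappears and the 12-agency problem remains. The plan does not say which coding applies.

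Two smaller points also stand. Rates above about 11.5% require outsiders to form one cluster, and the 12.8% also rests on an assumed offset and few runs. The interaction was simulated less often than the main effect, though the one repeat that covered it gave 7.8-10.8%.

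The remedy costs power as well as interval width. At OR 0.87 (latent ICC, equal sizes) simulated power was 23.3% uncorrected and 11.7% with Mancl-DeRouen and t10. Part of that loss is power that came only from the inflated level.

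**Conclusion.** The concern holds. The plan randomises 12 agencies and names no small-sample method. An uncorrected robust SE with 1.96 would give about 8-13% false positives for RRT, roughly twice the stated 5% (1.6 times at the low end), and about 9-11% for RRT by past attempt. The inflation is present at ICC 0, and the uncorrected rate stayed above 5% in every scenario run. The exact rate depends on the assumed ICC scale, agency-size spread, three agencies per cohort, coding of outsiders and form of the offset. The individually randomised CC comparison is not part of this finding. The point should be fixed: it concerns a named Aim 1 test, and the change is small.

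**What to change.** Prespecify small-sample inference for the two agency-level tests.

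- **RRT main effect:** a permutation test over the actual cohort allocation. With three agencies per cohort there are 12!/(3!)⁴ = 479,001,600/1,296 = 369,600 allocations, so a random sample of them is enough.
- **RRT interval and RRT by past attempt:** a bias-corrected sandwich SE with t on about 10 df, counted from the 12 agencies and not from the outsiders. Permuting cohorts tests for no RRT effect in anyone, so it does not isolate the interaction. Name one correction in advance. Mancl-DeRouen stayed at about 5% or below but is somewhat conservative; Kauermann-Carroll is narrower but reached 6.1%.
- **Coding:** state how subscribers outside the 12 agencies enter the clustering.
- **CC test:** leave as planned.
- **Optional, for precision only:** agency effects. Fixed effects cut the spread of the RRT estimate by 16-19% under the proportion-scale ICC, but raised it by 1-2% at latent ICC 0.01 and by 10% at ICC 0.

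The cost is SAP wording and a little programming, with no change to trial conduct. RRT intervals become 19-24% wider with Kauermann-Carroll and t10, or 25-37% wider with Mancl-DeRouen and t10. The RRT power statement should be rerun under the chosen test. Taking 88.3% at face value, power becomes Φ(3.15 − 1.96w) for widening factor w: about 79% at w = 1.19 and 68% at w = 1.37.

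The Data and Safety Monitoring Board paragraph (3.D3) gives a place for the change: "Our analysis plan will be reviewed and approved formally by the DSMB prior to the start of the study". The documents do not show whether that approval has already been given; if it has, an amendment is needed before outcome data are analysed.

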Training will use Stanley and Brown's well-established methods for videoconference training. SPI and C-SSRS training take about 6 hours total. Prior to the training, individuals will be emailed the SPI manual used in a previous intervention trial (SPIRIT).^{29,46} On the day of the training, information on the rationale for SPI, an overview of SPI, and the steps of SPI, with video clip demonstrations interspersed will be presented. We will provide an additional 30 minutes of training in reaching out to and re-engaging justice-involved individuals in BH care. After completing the online training and study of the written SPI manual, counselors will receive a 2.5 hour live training in SPI fidelity rating via webcam (i.e., it is live, but not in person). The group views and rates fidelity of SPI videos that vary in quality, and then discusses their answers. Drs. Stanley and Brown have found that practicing SPI fidelity assessment by critiquing SPI helped learners understand the SPI model and commit it to memory. C-SSRS training also includes video and live practice. These trainings will be recorded to ensure fidelity and consistency across the trainings. The audio/video files recorded during the meeting will be downloaded onto secure servers at Butler and Michigan State University (MSU).

Weekly reports: During the months BH agencies are assigned to the RRT intervention condition, they will receive weekly reports from CareSource with notifications of jail booking/release dates of any client seen by the agency in the 6 months prior to arrest. Reports will include instructions for how to reengage the client, and a reminder that the C-SSRS can be used for suicide risk assessment. Subscribers with any past (lifetime) suicide attempt documented in available claims data will be flagged for additional outreach and action, including SPI. These reports will be built into an existing, automated CareSource system that

sends jail booking/release data to BH agencies. This system is currently being piloted and refined by CareSource.

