For Study 2, we anticipate engaging at least 120 providers (~10 from each of the 12 participating behavioral health agencies). The study intervention will take place in Hamilton, Franklin, and Cuyahoga Counties in Ohio, with remote meetings between providers and investigators at Butler Hospital and MSU for training and implementation process supervision. Detailed implementation process notes will be generated from discussions between researchers and providers at the monthly meetings to characterize study implementation, offer feedback, and help problem-solve challenges.

Three sources of data will thus be used in this study: (1) input from focus group members, (2) implementation process notes and feedback from providers, and (3) claims data from subscriber recipients of the intervention or care as usual (CAU).

Per OHRP, this study does not constitute research on a vulnerable population (i.e., prisoners) for the following reasons:

- 1) The study activities include no interactions or interventions with incarcerated individuals through which their information is collected for research. Although the program may inspire

Date most recently revised (10/17/23)

Protocol Version: 9

Page 9 of 18

providers to communicate with prison populations in new ways consistent with known best practices, this would not be a research interaction or intervention through which information is obtained.

- 2) The study activities include no plans to obtain the private, identifiable information about any individual while incarcerated, or even to use such information for the research. While some information about the individuals' incarceration will be used, this is limited to publicly available information only.

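### The RRT effect is adjusted for one study-month effect shared with subscribers outside the 12 agencies, so about 55% of its information rests on an unstated parallel-trends assumption

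*Combined protocol and SAP*

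**What the plan says.** Section C4 (Data Analysis, Aim 1) describes the main effectiveness analysis as "planned as a comprehensive model (i.e., including all 43,000 subscribers"), a logistic regression for a medically treated attempt within six months of release. On time and condition it says "We will adjust for study month, and include indicator variables reflecting" three things: CC or usual care, inclusion in Study 2, and RRT or control. The past-year value of the outcome is a covariate, and agency clustering is handled by robust standard errors. No study month by Study 2 term, agency effect or Study 2-only analysis is given there or elsewhere. Whether month is categorical or linear is not said.

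Under Training behavioral health providers in section C2, the 12 agencies are randomly assigned to four cohorts and "they will begin at Months 4, 6, 8, and 10 of the CC intervention, respectively". For power, C4 states: "If we assume an intervention effect for Study 2 of 0.87 OR, we will have 88.3% power to detect this effect".

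**The concern.** RRT exposure is tied to calendar time: no agency has it in Months 1 to 3 and all have it from Month 10. Random step order protects comparisons between agencies within the same month. It does not protect a comparison of early with late months among agency clients; that needs a time trend, and the planned model takes the trend mostly from people who were not clients of these agencies.

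The documents give some reason to ask whether the trends run in parallel. Study 2 subscribers are recent clients of large behavioral health agencies. Section 3.A says "The study intervention will take place in Hamilton, Franklin, and Cuyahoga Counties in Ohio", whereas Study 1 is statewide. On the existing system that sends jail data to agencies, C2 says "This system is currently being piloted and refined by CareSource". Follow-up runs from an index release, and a re-arrest during follow-up does not lead to re-randomisation, so frequent cyclers will tend to enter early; this matters only if the depletion differs between the two groups.

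At stake is whether an RRT result can be presented as resting on the randomised roll-out.

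**Working it through.** **The plan's own figure.** Inputs from C4: OR 0.87, six-month risk 0.05, 6,000 Study 2 subscribers, two-sided 5%. OR 0.87 on 5% is a risk of 0.0435/(0.95 + 0.0435) = 4.38%. Two proportions with 3,000 per condition give 20.6% power. Simulating the planned model (12 agencies, ICC .01, past-attempt covariate, 1,000 runs) gives 20% with model-based and 22% with robust standard errors. The stated 88.3% would need about 22,959 per condition. A 21,500 v 21,500 split with 0.87 read as a risk ratio gives 89.1%, but the documents do not say how 88.3% arose.

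**Information on RRT.** Assumptions: three agencies per cohort, 12 release months, even inflow (500 Study 2 releases a month), categorical months. The exposed share e by month is 0, 0, 0, .25, .25, .5, .5, .75, .75, 1, 1, 1, with mean 0.5.

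- Within month, between agencies (randomised): 500 × Σe(1−e) = 500 × 1.25 = 625.
- Between months: 500 × Σ(e−0.5)² = 500 × 1.75 = 875. With the month effect shared with outsiders, 37/43 of this is kept: 753.
- Shared-month total: 625 + 753 = 1,378. Randomised share 625/1,378 = 45%; parallel-trends share 55%.
- Study 2-specific months: 625 (45% of 1,378). Agency terms remove a further 208, leaving 417 (30%).

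**Drift carried into the RRT coefficient.** For a linear drift of d per month in log odds among agency clients only, Σ(e−0.5)(m−6.5) = 15.5. The shift is 500 × 15.5 × (37/43)/1,378 = 4.84d, that is 4.84 of the 11 monthly steps, or 44%. By the same calculation 62% of a step at Month 7 and 47% of a step at Month 4 or 10 pass through. For a 12-month seasonal wave, 22% to 84% of the amplitude passes, with sign depending on phase.

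| Assumed drift per month | Change in odds, Month 1 to 12 | False RRT OR |
|---|---|---|
| 1% | exp(−0.11): −10% | exp(−0.0484) = 0.95 |
| 2% | exp(−0.22): −20% | exp(−0.0968) = 0.91 |
| 3% | exp(−0.33): −28% | exp(−0.1452) = 0.865 |

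**Simulation with no RRT effect, ICC .01** (1,000 runs without drift, 600 per drift setting). Cells give mean RRT OR and rejection rate with robust standard errors.

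| 12-month drift OR | Shared month | Study 2-specific months | Plus agency terms |
|---|---|---|---|
| none | 1.00, 11% | 1.00, 14% | 1.00, 12% |
| 0.8 | 0.90, 14% | 0.99, 9% | 1.00, 9% |
| 0.7 | 0.85, 25% | 1.00, 11% | 0.99, 10% |
| 0.5 | 0.74, 59% | 1.00, 10% | 1.00, 9% |

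Study 2-specific months remove the bias. The 11% without drift is a separate matter, from robust standard errors with only 12 agencies. With agency terms and model-based standard errors, rejection was 4% to 6% in every row.

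**Price of the change.** SE = 1/√(information × 0.05 × 0.95), with no agency heterogeneity: 0.124 shared, 0.184 with Study 2-specific months, 0.225 with agency terms as well. Power at OR 0.87 is Φ(0.139/SE − 1.96): 20%, 11% and 9%.

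**The case against.** The strongest defence is that pooling is a deliberate choice between bias and variance, which C4 justifies by power and by the ability to test the interaction of the two interventions. Taking linear-approximation standard errors at the plan's ICC, 0.155 shared and 0.225 with Study 2-specific months and agency terms, the shared-month model has the smaller mean squared error until the drift bias exceeds √(0.225² − 0.155²) = 0.16, which is 0.16/4.84, or about 3.4% per month. This stands as a reason to keep reporting the pooled model. It does not settle type I error, and it does not make the between-month part randomised.

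Several stronger readings are tempting and are not supported:

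- That any season, trend or case-mix change among agency clients becomes an RRT effect. Drift shared with outsiders is removed by the month term, fixed differences by the Study 2 indicator, and case mix captured by past-year attempts by that covariate. Only the part aligned with the roll-out passes through.
- That the RRT test has lost its randomised basis. About 45% of its information is still the random step order.
- That differential drift is present. Three counties and recent-client status are differences in level. The piloting remark does not say that non-study agencies will receive reports during the trial. No depletion difference is given.
- That excess rejection is all due to drift. At a 12-month drift OR of 0.8 it goes from 11% to 14%; most of the excess over 5% is the 12-cluster problem.

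Section D3 says the DSMB will approve the analysis plan before the start. A fuller specification may therefore exist, but these documents do not contain one.

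**Conclusion.** The point holds as a gap in the specification, not as a demonstrated bias. As written, about 55% of the information on RRT depends on parallel trends between agency clients and about 37,000 outsiders, and the plan neither states nor checks this. About 44% of a linear agency-specific drift, and up to most of a seasonal difference depending on its phase, would be read as an RRT effect. To imitate the whole target OR of 0.87 by linear drift alone, agency clients' odds would have to fall by about 27% to 28% relative to outsiders over the year (2.9% to 3% per month). Smaller drifts would distort the estimate in proportion, in either direction.

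The figures rest on equal cohorts, even inflow, 12 release months, categorical study month and a 5% risk. The drift sizes are assumptions shown as a range; nothing in the documents estimates them. The CC comparison is individually randomised and is not affected by this point.

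**What to change.** Keep the joint model for CC. For RRT and for RRT by past attempt, prespecify an analysis in which study month differs by Study 2 inclusion (study month × Study 2 terms), with agency terms in place of the single Study 2 indicator, and base the randomised RRT claim on it. Report the shared-month model beside it, labelled as relying on parallel trends. Add prior-12-month number of arrests, which C4 already extracts, as a covariate against case-mix drift. State a small-sample method for inference with 12 agencies.

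This is analysis-plan wording and needs no new outcome data. Either model does need the true study month. Section 3.A says patient dates will be randomly shifted before release to research staff, so the plan should say how study month reaches the analysts.

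The cost is precision. With no agency heterogeneity the RRT standard error rises from about 0.12 to 0.18 with Study 2-specific months and to about 0.22 with agency terms; information falls to 45% and 30%, and approximate power at OR 0.87 from about 20% to 11% and 9%. Since 88.3% is not reproduced even for the pooled model, restate RRT power for whichever model is primary.
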